8.2.2 Hypotheses/Estimation

Objectives and hypotheses of the study are stated in Section 3.0.

8.2.3 Analysis Endpoints

Efficacy and safety endpoints that will be evaluated are listed below.

8.2.3.1 Efficacy Endpoints

Primary

Progression-free survival (PFS) – RECIST 1.1 by BICR

Progression-free-survival is defined as the time from randomization to the first documented disease progression per RECIST 1.1 based on BICR or death due to any cause, whichever occurs first. See Section 8.2.5.1.1 for definition of censoring.

OS

OS is defined as the time from randomization to death due to any cause. Subjects without documented death at the time of the final analysis will be censored at the date of the last follow-up.

Secondary

Proportion progression free at 6 months and 12 months – RECIST 1.1 by BICR

The proportion progression free at 6 months and at 12 months is defined as the Kaplan-Meier estimate of the survival function for PFS at 6 months and 12 months, respectively. The progression-free status is based upon BICR per RECIST 1.1.

Objective Response Rate (ORR) – RECIST 1.1 by BICR

ORR is defined as the proportion of the subjects in the analysis population who have a CR or PR. Responses are based upon BICR per RECIST 1.1.

Exploratory

Duration of Response (DOR) – RECIST 1.1 by BICR

For subjects who demonstrated CR or PR, DOR is defined as the time from first documented evidence of CR or PR until disease progression or death, whichever occurs first.

Details of other exploratory endpoints will be provided in the sSAP.

8.2.3.2 Safety Endpoints

Safety measurements are described in Section 7 Trial Procedures.

8.2.3.3 PRO Endpoints

Global health status/quality-of-life assessment is based on the global health status/quality-of-life scales of the QLQ-C30 (items 29 and 30); pain is based on the pain multi-item scales of the EORTC QLQ-H&N35 (items 31-34), and TTD in swallowing is based on the swallowing multi-item scales of the EORTC QLQ-H&N35 (items 35-38).

TTD is defined as the time from baseline to first onset of PRO deterioration with confirmation (true deterioration). Here, true deterioration in the global health status/quality of life, pain, and swallowing endpoints is defined as a 10 points or greater worsening from baseline for each

multi-item scale [48; 52; 53] and confirmed by a second adjacent 10 or more deterioration from baseline under a right-censoring rule.

8.2.4 Analysis Populations

8.2.4.1 Efficacy Analysis Populations

The analysis of primary efficacy endpoints are based on the ITT population, i.e., subjects will be included in the treatment group to which they are randomized. If, upon the recommendation of DMC, the enrollment in pembrolizumab in combination with chemotherapy arm is paused and re-opened, subjects randomized during the pause will be excluded from the efficacy analysis population of pembrolizumab in combination with chemotherapy vs. standard treatment comparisons. Details on the approach to handling missing data are provided in Section 8.2.5 Statistical Methods.

8.2.4.2 Safety Analysis Populations

The All-Subjects-as-Treated (ASaT) population will be used for the analysis of safety data in this study. The ASaT population consists of all randomized subjects who received at least one dose of study treatment. Subjects will be included in the treatment group corresponding to the study treatment they actually received for the analysis of safety data using the ASaT population. For most subjects this will be the treatment group to which they are randomized. Subjects who take incorrect study treatment for the entire treatment period will be included in the treatment group corresponding to the study treatment actually received. Any subject who receives the incorrect study medication for one cycle but receives the correct treatment for all other cycles will be analyzed according to the correct treatment group and a narrative will be provided for any events that occur during the cycle for which the subject is incorrectly dosed.

At least one laboratory or vital sign measurement obtained subsequent to at least one dose of study treatment is required for inclusion in the analysis of each specific parameter. To assess change from baseline, a baseline measurement is also required.

8.2.4.3 PRO Analysis Population

The PRO analyses are based on the PRO full analysis set population, defined as subjects who have at least one PRO assessment available and have received at least one dose of the study medication.

8.2.5 Statistical Methods

This section describes the statistical methods that primarily address the primary and secondary objectives. Methods related to exploratory objectives will be described in the sSAP.

Statistical testing and inference for safety analyses are described in 8.2.5.2. Efficacy results that will be considered to be statistically significant after consideration of the strategy for controlling the Type I error are described in Section 8.2.6, Multiplicity. Nominal p-values may be computed for other efficacy analyses as a measure of strength of association between the endpoint and the treatment effect rather than formal tests of hypotheses.

8.2.5.1 Statistical Methods for Efficacy Analyses

8.2.5.1.1 Progression-Free Survival (PFS)

The nonparametric Kaplan-Meier method will be used to estimate the PFS curve in each treatment group. The treatment difference in PFS will be assessed by the stratified log-rank test. A stratified Cox proportional hazard model with Efron's method of tie handling will be used to assess the magnitude of the treatment difference (i.e., hazard ratio) between the treatment arms. The hazard ratio and its 95% CI from the stratified Cox model with Efron's method of tie handling and with a single treatment covariate will be reported. The same stratification factors used for randomization (see Section 5.4) will be used as the stratification factors in both the stratified log-rank test and the stratified Cox model for the analyses in all subjects and in subjects with PD-L1 CPS 1. For analyses in the PD-L1 CPS 20 subgroup, HPV status and ECOG status will be used as the stratification factors. In the event that there are low event counts (<5) in one or more strata, for the analysis purpose, strata will be combined to ensure sufficient number of events in each stratum. The order of stratification factors to combine strata over is as follows:

1. Eliminate ECOG performance score from analysis stratification, leaving stratification by PD-L1 tumor expression defined by TPS and HPV status;
2. Eliminate both ECOG performance score and HPV status from analysis stratification, leaving stratification by PD-L1 tumor expression defined by TPS;
3. Eliminate all stratification factors.

Since disease progression is assessed periodically, PD can occur any time in the time interval between the last assessment where PD was not documented and the assessment when PD is documented. For the primary analysis, for the subjects who have PD, the true date of disease progression will be approximated by the date of the first assessment at which PD is objectively documented per RECIST 1.1 by central imaging vendor, regardless of discontinuation of study drug. Death is always considered as a confirmed PD event. Sensitivity analyses will be performed for comparison of PFS based on investigator's assessment.

In order to evaluate the robustness of the PFS endpoint per RECIST 1.1 by central imaging vendor, we will perform 2 sensitivity analyses with a different set of censoring rules. The first sensitivity analysis is the same as the primary analysis except that data for any subject who misses more than one disease assessment (with or without a subsequent death or progression) are censored at the last disease assessment prior to missing visits. The second sensitivity analysis is the same as the primary analysis except that it considers discontinuation of treatment or initiation of an anticancer treatment subsequent to discontinuation of study-specified treatments, whichever occurs later, to be a PD event for subjects without documented PD or death. If a subject meets multiple criteria for censoring, the censoring criterion that occurs earliest will be applied. The censoring rules for primary and sensitivity analyses are summarized in [Table 18](#).

Table 18 Censoring Rules for Primary and Sensitivity Analyses of PFS

Situation	Primary Analysis	Sensitivity Analysis 1	Sensitivity Analysis 2
No PD and no death; new anticancer treatment is not initiated	Censored at last disease assessment	Censored at last disease assessment	Censored at last disease assessment if still on study therapy; progressed at treatment discontinuation otherwise
No PD and no death; new anticancer treatment is initiated	Censored at last disease assessment before new anticancer treatment	Censored at last disease assessment before new anticancer treatment	Progressed at date of new anticancer treatment
No PD and no death; ≥ 2 consecutive missed disease assessments	Censored at last disease assessment	Censored at last disease assessment prior to ≥ 2 consecutive missed visits	Censored at last disease assessment
PD or death documented after ≤ 1 missed disease assessment	Progressed at date of documented PD or death	Progressed at date of documented PD or death	Progressed at date of documented PD or death
PD or death documented at any time after ≥ 2 missed disease assessments	Progressed at date of documented PD or death	Censored at last disease assessment prior to the ≥ 2 missed disease assessment	Progressed at date of documented PD or death

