5.4 Stratification

Randomization will be stratified according to the following factors:

1. PD-L1 tumor expression as determined by PD-L1 immunohistochemistry (strongly positive vs. not strongly positive)
Note: *Strongly positive* includes those subjects whose tumor expression levels are $\geq 50\%$. *Not strongly positive* includes those subjects whose tumor expression levels are $< 50\%$, or are not able to be determined for any reason.
2. HPV status for oropharynx cancer as determined by p16 immunohistochemistry (IHC) (positive vs. negative); HPV status for subjects without oropharynx cancer (e.g. cancers of the oral cavity, hypopharynx and larynx) is considered HPV negative.

3. Eastern Cooperative Oncology Group (ECOG) Performance Scale (0 vs. 1)

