8.2.5.1.2 Overall Survival (OS)

The nonparametric Kaplan-Meier method will be used to estimate the survival curves. The treatment difference in survival will be assessed by the stratified log-rank test. A stratified Cox proportional hazard model with Efron's method of tie handling will be used to assess the magnitude of the treatment difference (i.e., the hazard ratio). The hazard ratio and its 95% CI from the stratified Cox model with a single treatment covariate will be reported. The same stratification factors used for randomization (see Section 5.4) will be used as the stratification factors in both the stratified log-rank test and the stratified Cox model for the analyses in all subjects and in subjects with PD-L1 CPS 1. For analyses in the PD-L1 CPS 20 subgroup, HPV status and ECOG status will be used as the stratification factors. In the event that there are low event counts (<5) in one or more strata, for the analysis purpose, strata will be combined to ensure sufficient number of events in each stratum. The order of stratification factors to combine strata over is the same as specified for PFS analysis.

Since subjects in the standard therapy arm are expected to discontinue treatment earlier compared to subjects in the pembrolizumab arms, and they may switch to another anti-PD-1 treatment following confirmation of progressive disease, adjustment for the effect of crossover on OS may be performed based on recognized methods, e.g. the Rank Preserving Structural Failure Time model proposed by Robins and Tsiatis (1989) [55], two stage model, etc., based

on an examination of the appropriateness of the data to the assumptions required by the methods.

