8.2.5.1.4 Objective Response Rate (ORR)

The stratified Miettinen and Nurminen's method will be used for comparison of the objective response rates between the treatment groups. The difference in ORR and its 95% CI from the stratified Miettinen and Nurminen method with strata weighting by sample size will be provided. The same stratification factors used for randomization (see Section 5.4) will be used as the stratification factors in the analysis of all subjects and subjects with PD-L1 CPS 1. For analyses in the PD-L1 CPS 20 subgroup, HPV status and ECOG status will be used as the stratification factors. In the event that there are low responses (<5) in one or more strata, for the analysis purpose, strata will be combined to ensure sufficient number of responses in each stratum. The order of stratification factors to combine strata over is the same as specified for PFS analysis. Sensitivity analyses will be performed for comparison of ORR based on investigator's assessment.

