8.2.7 Sample Size and Power Calculation

The study plans to randomize approximately 825 subjects with 1:1:1 ratio into the treatment groups of pembrolizumab monotherapy, a combination of pembrolizumab with chemotherapy and standard treatment, stratified by PD-L1 expression (strongly positive vs. not strongly positive), HPV status (HPV+ vs. HPV-), and ECOG performance status (0 vs. 1). The prevalence of PD-L1 positive subpopulation is projected to be 50% for PD-L1 CPS 20 and 80% for the PD-L1 CPS 1 subpopulation.

Two interim efficacy analyses are planned in this study. A Hwang-Shih-DeCani alpha-spending function with gamma parameter (-4) is constructed to implement group-sequential efficacy boundaries for each PFS and each OS hypothesis.

PFS:

Two PFS analyses are planned at interim analyses 1 and 2. The PFS hypotheses will be tested at interim analysis 1, and a second test of PFS, which will be the final PFS analyses, may occur at interim analysis 2 only if superior PFS is not declared at interim analysis 1. At the time of the final PFS analysis:

H1, H4: for subjects with PD-L1 CPS 20, it is expected that approximately 237 PFS events will have been observed between one experimental treatment and standard treatment.

The study has 90% power with each experimental treatment (pembrolizumab monotherapy [H1] or pembrolizumab in combination with chemotherapy [H4]) to detect a hazard ratio of 0.58 vs. standard treatment at alpha = 0.19% (one-sided).

H2, H5: for subjects with PD-L1 CPS 1, it is expected that approximately 378 PFS events will have been observed between one experimental treatment and standard treatment.

The study has 98.6% power with each experimental treatment (pembrolizumab monotherapy [H2] or pembrolizumab in combination with chemotherapy [H5]) to detect a hazard ratio of 0.59 vs. standard treatment at alpha = 0.19% (one-sided). (Note that H2 will be tested only if H1 is rejected and H5 will be tested only if H4 is rejected.)

H3: for all subjects: it is expected that approximately 474 PFS events will have been observed between pembrolizumab monotherapy and standard treatment. The study has 99.6% power with pembrolizumab monotherapy to detect a hazard ratio of 0.6 vs. standard treatment at alpha = 0.19% (one-sided). (Note that H3 will be tested only if H1 and H2 are rejected under the multiplicity strategy.)

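### In the all-subjects and CPS 1 analyses, one stratum with fewer than 5 events removes ECOG from every stratum; merging only the sparse stratum avoids a small, conditional power loss at no cost

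*Combined protocol and SAP*

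**What the plan says.** Section 5.4 stratifies randomisation by PD-L1 (TPS 50% cutpoint), HPV status and ECOG (0 or 1). Section 8.2.5.1.1 carries these factors into the PFS analysis: they "will be used as the stratification factors in both the stratified log-rank test and the stratified Cox model for the analyses in all subjects". The CPS 1 analyses are treated the same way, while the CPS 20 analyses use HPV and ECOG only.

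The collapsing rule follows: "In the event that there are low event counts (<5) in one or more strata, for the analysis purpose, strata will be combined". One sparse stratum is enough. The first listed step is "Eliminate ECOG performance score from analysis stratification, leaving stratification by PD-L1 tumor expression defined by TPS and HPV status"; the second also removes HPV, and the third removes everything. Nothing limits the collapse to the sparse stratum. The text also does not say whether events are counted over the two compared arms or over all three.

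Section 8.2.5.1.2 applies this to OS ("The order of stratification factors to combine strata over is the same as specified for PFS analysis"). Section 8.2.5.1.4 applies it to ORR with a trigger in responses: "In the event that there are low responses (<5) in one or more strata".

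**The concern.** With 2 × 2 × 2 = 8 strata, the rarest cell (TPS ≥50%, p16-positive, ECOG 0) may hold very few subjects. If that cell alone falls below 5 events, the plan gives up ECOG in the other seven strata, which may be well filled. Neither the stratified log-rank test nor the stratified Miettinen and Nurminen method needs this, since a sparse cell can be merged with a neighbour and the rest left alone.

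Omitting a prognostic factor that was balanced by randomisation pulls the hazard ratio toward 1 and costs power. Whether this happens depends on chance counts in one small cell. Because counts grow, the same hypothesis could be tested without ECOG at IA1 and with it at the final analysis.

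**Working it through.** **1. The plan's own power.** Inputs from section 8.2.7 for H10/H14: 455 deaths, HR 0.7, one-sided alpha 0.7%.

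Φ(√455/2 × |ln 0.7| − z₀.₉₉₃) = Φ(10.665 × 0.3567 − 2.457) = Φ(1.347) = 91.1%, against 90.4% stated. The formula is fixed-sample and the plan is group-sequential, so this agrees. With the final bound in Table 23 (Z = 2.5641), the final look alone gives Φ(3.804 − 2.564) = Φ(1.240) = 89.2%. The simulations in step 4 should be read against that figure.

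**2. How small is a stratum with at most 4 events?** Section 8.2.7 says: "The study plans to randomize approximately 825 subjects with 1:1:1 ratio into the treatment groups". That is 275 per arm and 550 per pairwise comparison, or 440 in CPS 1 at 80% prevalence. At the average event fraction, the stratum's share is 4 ÷ (events/N) ÷ N = 4 ÷ events. Event counts are from section 8.2.9.2.

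| Analysis | All subjects | CPS 1 |
|---|---|---|
| PFS IA1 | 4/423 = 0.95% | 4/337 = 1.19% |
| PFS IA2 | 4/474 = 0.84% | 4/378 = 1.06% |
| OS IA1 | 4/352 = 1.14% | 4/278 = 1.44% |
| OS IA2 | 4/421 = 0.95% | 4/332 = 1.20% |
| OS final | 4/455 = 0.88% | 4/359 = 1.11% |

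A cell with half the average hazard has a larger share: 1.2–1.7% at PFS IA1, OS IA1 and OS final, except CPS 1 OS at IA1, where it is 2.2%. These shares do not apply to ORR.

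**3. How often does the rule fire?** The documents give no prevalences, so these are assumptions: TPS ≥50% 20%, p16-positive 20%, ECOG 0 40%; OS hazard ratio 1.7 for ECOG 1 vs 0 and 0.6 for p16-positive. The rarest cell then has 550 × 0.2 × 0.2 × 0.4 = 8.8 subjects. Simulation set-up: 550 subjects, stratified randomisation, exponential OS with a median of about 10 months, 21-month accrual, looks at 30, 38 and 44 months.

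- All subjects, at least one stratum with fewer than 5 deaths: 75%, 56% and 45% at IA1, IA2 and final. Repeat runs gave 40% and 42% at final.
- Final, varying p16 only: 24% at p16 25%, 74% at p16 15%.
- Final with TPS 30%: 11% at p16 20%, 3% at p16 25%.

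A simpler binomial calculation took the smallest cell alone, at average risk, over a wider grid (TPS 15–30%, p16 15–34%, ECOG 0 30–40%). At the final OS analysis it ran from under 1% to about 80%.

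**4. Power when the rule fires.** Simulated final look for H10/H14 (HR 0.7, bound Z = 2.5641); compare within rows.

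| Assumed ECOG HR | 8 strata | ECOG dropped | Only sparse cell merged | Loss from dropping ECOG (points) |
|---|---|---|---|---|
| 1.3 | 89.1% | 88.9% | 89.2% | 0.2 |
| 1.5 | 88.1% | 87.5% | 88.2% | 0.6 |
| 1.7 | 88.7% | 86.5% | 88.8% | 2.2 |
| 2.0 | 86.3% | 82.4% | 86.2% | 3.9 |

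Other runs gave losses of 2.2 to 2.9 points at 1.7 and 3.6 to 4.7 at 2.0. With ECOG dropped, the mean estimated HR moved from about 0.70 to 0.703 (ECOG HR 1.5) or 0.715 (2.0). For PFS, H6 lost nothing at ECOG HR 1.3 and went from 97.4% to 96.1% at 1.7; H3 went from 99.7% to 99.4%.

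**5. Type I error, superiority.** At nominal 2.5% one-sided: 2.57% with 8 strata, 2.57% with the local merge, 2.03% with ECOG dropped.

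**The case against.** The rule is pre-specified, fully ordered and applied identically to PFS and OS. It contradicts nothing and does not inflate superiority error. The loss depends on an assumed ECOG effect and arises only when the rule fires: at a 45% trigger chance, a 2.2-point loss averages 0.45 × 2.2 = 1.0 point. All of that stands, and it limits this to an efficiency point.

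Four stronger readings are tempting.

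- *CPS 1 is much more exposed because it is smaller.* Keeping TPS ≥50% at 20% of 440 gives 89/75/66% at the three looks. But section 4.1.3 describes CPS as counting tumour and inflammatory cells and TPS as tumour cells alone, so a TPS ≥50% tumour should also be CPS ≥1. The 20% × 550 = 110 such subjects are then 110/440 = 25% of CPS 1, and the rarest cell stays at 8.8. The chances become 77/56/45%, against 73/52/42% for all subjects in the same run.
- *The dual-primary tests lose power generally.* Of the 2.5% alpha, 2 × 0.19 + 2 × 0.7 = 1.78% starts on CPS 20 hypotheses (section 8.2.6), which do not use the three-factor stratification. H10 and H14 are reached only after earlier rejections.
- *Noninferiority error is inflated.* Attenuation toward 1 is not automatically conservative for H9/H13. At a true HR of 1.2, dropping ECOG moved the mean estimate to 1.190 (ECOG HR 1.7) or 1.185 (2.0), and error at the final bound was 0.65–0.68% against 0.55–0.58%. With simulation error of about 0.06 points, this is worth noting but does not establish inflation.
- *Local merging would fix stratification across looks.* It would not, because it is also triggered by counts. It only confines the change to the sparse cell.

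**Conclusion.** The point holds as an avoidable inefficiency, not as an error in the plan. In the three-factor analyses, a stratum holding about 0.8–1.4% of the comparison (up to about 2% with good prognosis) can remove a randomisation factor from all eight strata. The chance at the final all-subjects OS analysis is very uncertain: about 3% to 75% in the simulated scenarios, with CPS 1 similar. When the rule fires, H10/H14 lose about 0, under 1, 2–3 or 4 points of final-look power at ECOG hazard ratios of 1.3, 1.5, 1.7 or 2.0. PFS tests lose about 1 point or less.

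These sizes rest on assumed prevalences and prognostic effects that the documents do not supply, and on counting events over the two compared arms. No ORR effect was computed.

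**What to change.** Replace the three-step elimination list in section 8.2.5.1.1 with:

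> A stratum with fewer than 5 events (counted over the two compared arms pooled) is merged with the stratum that differs only in ECOG. If the merged stratum is still below 5, it is merged with both ECOG levels of the other HPV category in the same TPS group; if still below 5, with the other TPS group. All other strata keep the stratification factors specified for that population.

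Apply it to PFS, OS and ORR, with responses in place of events for ORR. In CPS 20, where TPS is not a stratification factor, the sequence ends at the HPV step.

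The cost is a short paragraph of SAP text and a few lines of code. In the simulations the local merge kept the power of the full stratification and its type I error for superiority. Stratification may still differ between looks, but only in the sparse cell.
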